7.2.5 Visit 5 (2 months after the first infusion) Procedures

- Record vital signs, including blood pressures, pulse, and temperature
- Complete the BVAS/WG Score
- Complete the VCRC-Disease activity and Transition Assessment by the investigator
- Draw blood for clinical laboratory tests
- Collect samples for mechanistic biomarker assessments
- Collect a clean-catch, mid-stream urine sample for urinalysis
- Perform VDI assessment
- Record medications used
- Review glucocorticoid use
- Assess adverse events

7.2.6 Visit 6 (Month 4) Procedures

- Record vital signs, including blood pressures, pulse, and temperature
- Complete the BVAS/WG Score
- Complete the VCRC-Disease activity and Transition Assessment by the investigator
- Draw blood for clinical laboratory tests
- Collect samples for mechanistic biomarker assessments
- Collect a clean-catch, mid-stream urine sample for urinalysis
- Record medications used
- Review glucocorticoid use
- Assess adverse events

7.2.7 Visit 7 (Month 6) Procedures

- Record vital signs, including blood pressures, pulse, and temperature
- Perform a 12-lead ECG measurement
- Complete the BVAS/WG Score
- Complete GTI assessment.
- Collect a clean-catch, mid-stream urine sample

- Perform VDI assessment
- Complete AAV-PRO by the patient
- Complete the VCRC-Disease activity and Transition Assessment by the investigator
- Draw blood for clinical laboratory tests
- Collect samples for mechanistic biomarker assessments
- Record medications used
- Assess adverse events

7.3 Maintenance Period

7.3.1 Visits 8, 9 and 10 (Months 9, 12, and 15) Procedures

Study participants will be scheduled to complete a clinic visit every 3 months.

- Record vital signs, including blood pressures, pulse, and temperature
- Complete the BVAS/WG Score
- Complete the VCRC-Disease activity and Transition Assessment by the investigator
- Complete AAV-PRO by the patients at month 12
- Complete GTI assessment
- Perform VDI assessment
- Draw blood for clinical laboratory tests
- Collect samples for mechanistic biomarker assessments
- Collect a clean-catch, mid-stream urine sample for urinalysis
- Record medications used
- Assess adverse events

7.3.2 Visits 11 (Month 18) Procedures

Study participants will be scheduled to complete a final clinic visit.

- Record vital signs, including blood pressures, pulse, and temperature
- Complete the BVAS/WG Score
- Complete the VCRC-Disease activity and Transition Assessment by the investigator
- Complete AAV-PRO by the patient
- Complete GTI assessment
- Perform VDI assessment
- Draw blood for clinical laboratory tests
- Collect samples for mechanistic biomarker assessments
- Perform a 12-lead ECG measurement

- Collect a clean-catch, mid-stream urine sample for urinalysis
- Record medications used
- Assess adverse events
- Complete End of Study record

7.3.3 Visit 99 (Unscheduled Visit) Procedures

- Record vital signs, including blood pressures, pulse, and temperature
- Complete the BVAS/WG Score
- Complete the VCRC-Disease activity and Transition Assessment by the investigator
- Complete AAV-PRO by the patients
- Complete GTI assessment
- Draw blood for clinical laboratory tests
- Collect samples for mechanistic biomarker assessments
- Record medications used
- Assess adverse events

7.4 Early Termination Procedures

Patients who withdraw consent early, procedures outlined for the Month 18 visit (V11) should be completed.

7.5 Study Activities for Treatment Failure Patients

8 PATIENTS WILL BE CONSIDERED TREATMENT FAILURES IF THE GLUCOCORTICOID DOSE HAS TO BE INCREASED EITHER DURING THE PREDNISONE TAPER OR AFTER REMISSION BECAUSE OF A DISEASE RELAPSE OR IF ANY OTHER TREATMENT FOR ANCA-ASSOCIATED VASCULITIS IS PRESCRIBED TO TREAT A DISEASE RELAPSE. THE PATIENTS WHO EXPERIENCED TREATMENT FAILURE WITH DETECTABLE B CELLS (≥ 5 CELLS/ML) WILL BE OFFERED OPEN-LABEL OBINUTUZUMAB ACCCOMPANIED ONE TO THREE INTRAVENOUS METHYLPREDNISOLONE PULSES (1000 MG EACH) STARTING ON OR WITHIN 10 CALENDAR DAYS OF OBINUTUZUMAB FOLLOWED BY ORAL GLUCOCORTICOID DOSING AT THE DISCRETION OF THE INVESTIGATOR (BUT NOT TO EXCEED THE ORIGINAL SPECIFIED GLUCOCORTICOID TAPERING REGIMEN) TO CONTROL THE DISEASE. PATIENTS WHO EXPERIENCE A TREATMENT FAILURE AND B CELLS ARE STILL DEPLETED SHOULD BE TREATED ACCORDING TO BEST MEDICAL JUDGMENT. PATIENTS WHO RESPOND TO THE RE-TREATMENT AND ACHIEVE CLINICAL REMISSION WILL ENTER THE MAINTENANCE PHASE AND BE EVALUATED EVERY 3 MONTHS UNTIL THE STUDY COMPLETES. ANY PATIENT WHO EXPERIENCES TREATMENT FAILURE SHOULD CONTINUE WITH STUDY FOLLOW-UP VISITS PER THE SCHEDULE OF ASSESSMENTS THROUGH THE END OF STUDY. QUALITY CONTROL AND ASSURANCE

The clinical research facility will be monitored by the study monitor to ensure correct performance of the study procedures and to ensure that the study is conducted according to the protocol and relevant regulatory requirements. CRF entries will be verified with the source documentation.

Quality control principles will be applied throughout the performance of this study by following the Standard Operating Procedures (SOPs) of the contract research organization (CRO) and the Principal Investigator. Review procedures will be implemented at the CRO for all documents that are generated in relation to the study.

The laboratory testing will be performed by a CLIA certified central laboratory to ensure the laboratory values are determined consistently.

The overall procedures for quality assurance of clinical trial data, including data collection and management, will be described in the Data Management Plan.

Accurate and reliable data collection will be assured by verification and crosscheck of the eCRF against the Investigator's records by the trial monitor (source document verification), and the maintenance of drug accountability by the Investigator.

Data for this trial will be recorded in the trial electronic case report forms (eCRFs) using Medidata RAVE. The data will be entered by the trial center from the source documents into the eCRF or will be loaded from other files.

A comprehensive validation check program will verify the data and discrepancy reports will be generated accordingly for resolution by the Investigator. All discrepant data will be resolved in the EDC database and data entered in the database will be independently compared with the original Investigator's records.

For classification purposes, preferred terms will be assigned to the original terms recorded on the eCRF, using MedDRA for AEs, diseases and surgical and medical procedures, and the WHO drug dictionary for drug and herbal treatments.

9 PLANNED STATISTICAL METHODS

9.1 General Considerations

The following sections provide a summary of the planned analysis of the trial, but a full statistical analysis plan (SAP) will be developed as a separate document and will become the final plan prior to primary efficacy 6-month endpoint analysis. All statistical analyses will be performed using SAS Version 9.4 or higher.

Data summaries will use descriptive statistics (number of subjects [N], mean, standard deviation [SD], median, quartiles, minimum, and maximum) for continuous variables, and frequency and percentage of subjects in each category for categorical and ordinal variables. If there are missing values, the number missing will be presented, but without a percentage.

Unless otherwise specified, all tests will be two-tailed using a 0.05 level of significance. All confidence intervals (CIs) will be two-sided 95% confidence intervals.

9.2 Determination of Sample Size

PRRR is an exploratory proof-of-concept study to evaluate the potential utility of obinutuzumab for the treatment of PR3-ANCA associated vasculitis. We anticipate the proportion of patients in the obinutuzumab group that will achieve complete remission and ANCA negativity is 0.55 and the proportion of patients in the rituximab group that will achieve complete remission and ANCA negativity is 0.30; the planned sample size of 30 patients in two equal size groups is not powered to test the hypothesis that obinutuzumab is superior to rituximab. No sensitivity analyses (e.g., to account for missing data) and no adjustment for multiple comparisons will be conducted. Nominal p-values will be used to examine any trends in the endpoint.

9.3 Analysis Populations

9.3.1 Intention-to-treat Analysis Set:

All subjects who are randomized regardless of treatment adherence or availability of follow up data will be included in the intention-to-treat analysis set (ITT). All analyses of the ITT will be based on each subject's assigned treatment. The ITT will be the secondary analysis set used for the efficacy endpoint analyses where specified.

9.3.2 Modified Intention-to-Treat Analysis Set

All subjects who are included in the intention-to-treat analysis set (ITT), have received any amount of the study drug will be included in the modified intention-to-treat (mITT) analysis set. The mITT will be the primary analysis set used for the efficacy endpoint analyses.

9.3.3 Safety Analysis Set

All subjects who are randomized and have received any amount of the study drug will be included in the Safety Analysis Set. Safety analyses will be based on the medication that was actually dispensed to each patient. This is the primary analysis set for safety.

9.4 Demographics and Baseline Characteristics

Patients must meet all inclusion criteria and none of the exclusion criteria in order to participate in the study. Demographic characteristics include age, gender, race, ethnicity, and study center. Summary descriptive statistics will include counts and percentages for discrete variables and estimation of means, standard deviations, medians, quartiles, minimum and maximum for continuous metrics. These analyses will be carried out for the ITT, mITT and safety analysis sets.

9.5 Primary Efficacy Endpoint

The primary efficacy endpoint is defined as the proportion of patients achieving complete remission and ANCA negativity at month 6. Complete remission is defined as:

- BVAS/WG of 0; and
- No requirement for glucocorticoids for treatment of PR3-ANCA associated vasculitis beyond the prescribed 16-week prednisone taper.

Patients must achieve a complete remission as defined above and be ANCA-negative at month 6 in order to meet the primary efficacy endpoint.

The primary efficacy analysis is to compare the proportion of patients assigned to the obinutuzumab group who meet the primary efficacy endpoint criteria at month 6 to the proportion of patients assigned to the rituximab group who meet the primary efficacy endpoint criteria at month 6.

Descriptive statistics (number and percent of subjects meet the primary efficacy endpoint criteria) will be reported by treatment group.

The following null (H_0) and alternative (H_a) hypotheses will be tested using Fisher's Exact test the mITT analysis set:

$$H_0: \pi_{\text{obinutuzumab}} - \pi_{\text{rituximab}} = 0$$
$$H_a: \pi_{\text{obinutuzumab}} - \pi_{\text{rituximab}} \neq 0$$

π obinutuzumab: proportion of patients assigned to the obinutuzumab group who achieve complete remission and ANCA negativity in 6 months

II rituximab: proportion of patients assigned to the rituximab group who achieve complete remission and ANCA negativity in 6 months

The above null hypothesis will be tested using Fisher's Exact test. Two-sided Newcombe-corrected 95% confidence intervals of the risk difference between treatments with respect to the primary efficacy endpoint success rate will also be presented. It is not expected that the null hypothesis will be rejected at a two-sided 0.05 level of significance given the proof-of-concept nature of the study and given the small sample size; trends seen between treatment groups in the primary endpoint rate will be used to define future studies.

The above analyses on the primary efficacy endpoint success rate will be performed when all subjects have completed 6 months of follow-up (or would have completed 6 months of follow-up) had they not withdrawn.

9.6 Primary Safety Endpoints

Safety data includes adverse events (AEs), vital signs, ECG results and clinical lab results including serum chemistry, hematology, and urinalysis. Observed data will be described as counts and percentages for discrete variables and estimation of means, standard deviations, medians, inter-quartile range, minimum and maximum for continuous metrics. All patients who are randomized and dispensed double-blind study medication will be included in the safety analysis. Data collected from subjects who were enrolled but not randomized will be presented separately. All safety data will be presented in by-subject listings and included in the clinical trial report.

Adverse events will be mapped to preferred term and body system using the Medical Dictionary for Regulatory Activities (MedDRA) dictionary. The number and percentage of patients reporting treatment emergent adverse events will be presented overall, by MedDRA System Organ Class (SOC) and by MedDRA Preferred Term (PT) within each SOC. A treatment emergent adverse event is an event that begins or worsens in severity at or after the start of randomized treatment. This analysis will be repeated for serious treatment emergent adverse events, for treatment emergent adverse events of special interest, (see list provided below) and for treatment emergent adverse events at least possibly related to study drug. In addition, the number and percent of patients with treatment emergent adverse events will be presented by severity for each SOC and PT. Patients experiencing more than one treatment emergent adverse event within a given SOC and PT will be assigned to most severe category experienced.

Adverse event listings will be provided for the following subsets:

- All treatment emergent AEs
- All TEAEs at least possibly related to the investigational product
- Serious TEAEs
- TEAEs leading to dosing discontinuation or study withdrawal
- GTI scores (Cumulative Worsening Scores and Aggregate Improvement Scores (McDowell et al., 2020)

The adverse events of special interest include:

- Infusion related reactions (IRR)
- Neutropenia
- Thrombocytopenia
- Worsening of pre-existing cardiac conditions
- Infections (infections include all PTs in the SOC of Infections and Infestations)
- Hepatitis B reactivation
- Progressive multifocal leukoencephalopathy (PML)

9.7 Secondary Endpoints

No sensitivity analyses and adjustment for multiple comparisons will be conducted for the secondary endpoints. Nominal p-values will be used to examine any trends in these endpoints. The analyses will be carried out on the ITT and mITT populations, with no imputation for missing data. The secondary endpoints are:

- To compare the proportion of subjects who achieve sustained complete remission at months 6, 12 and 18 (BVAS/WG = 0 without glucocorticoids) by administration of obinutuzumab or rituximab. These comparisons will be carried out using Fisher's Exact test.
- To compare the time to treatment failure through month 18 by administration of obinutuzumab or rituximab; patients will be considered treatment failures if the glucocorticoid dose has to be increased because of a disease relapse either during the prednisone taper or after the remission is achieved. A disease relapse is defined as an increase in the BVAS/WG of 1 point or more accompanied by a decision on the part of the investigator to increase treatment for PR3-AAV. Time-to-treatment failure will be compared between treatments using the log-rank test; Kaplan-Meier plots of time to treatment failure through 18 months will be generated for each randomized treatment group; patients not experiencing treatment failure will be censored at last known follow-up for these analyses.

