The primary objective of this study is to determine the proportion of patients achieving both complete remission and seronegativity for ANCA at 6 months. Complete remission is defined as a Birmingham Vasculitis Activity Score for Wegener's Granulomatosis (BVAS/WG) of 0 without glucocorticoids beyond the prescribed prednisone taper. Seronegativity for ANCA is defined as a negative test for antibodies directed against serine proteinase 3 (i.e., a negative PR3-ANCA assay).

Secondary Objectives:

The secondary objectives of this study are:

- To compare the proportion of subjects who achieve sustained complete remission at month 6 after administration of obinutuzumab or rituximab. **Complete remission is defined as BVAS/WG = 0 without glucocorticoids.**
- To compare the proportion of subjects who achieve sustained complete remission at month 12 after administration of obinutuzumab or rituximab.
- To compare the proportion of subjects who achieve sustained complete remission at month 18 after administration of obinutuzumab or rituximab.
- To compare the time to treatment failure through month 18 by administration of obinutuzumab or rituximab; Patients will be considered treatment failures if the glucocorticoid dose has to be increased at any point during the 18-month study period because of a disease relapse. **Disease relapse is defined as an increase in the BVAS/WG of ≥ 1 point accompanied by a decision on the part of the investigator to increase treatment for PR3-AAV**

Follow-up in the trial will continue until all patients have been followed for 18 months.

Exploratory Objectives:

The exploratory objectives are to compare between the two treatment groups for following outcomes:

- The number of disease relapses as defined as an increase in the BVAS/WG of ≥ 1 point accompanied by a decision on the part of the investigator to increase treatment for PR3-AAV.
- The Glucocorticoid Toxicity Index (GTI) scores (Cumulative Worsening Score and Aggregate Improvement Score) over time;
- The cumulative glucocorticoid dose;
- The number of severe relapses. ***Severe relapse is defined as at least one major BVAS/WG item or a BVAS/WG ≥ 3 and the investigator deems standard treatment for severe disease is necessary.***
- The changes from baseline in Vasculitis Damage Index (VDI) over time;
- The time to clinical remission;
- The changes in estimated glomerular filtration rate (eGFR);

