2.2 Secondary Objectives

The secondary objectives of this study are:

- To compare the proportion of subjects who achieve sustained complete remission at month 6 after administration of obinutuzumab or rituximab. ***Complete remission is defined as BVAS/WG = 0 without glucocorticoids***
- To compare the proportion of subjects who achieve sustained complete remission at month 12 after administration of obinutuzumab or rituximab.
- To compare the proportion of subjects who achieve sustained complete remission at month 18 after administration of obinutuzumab or rituximab.

- To compare the time to treatment failure through month 18 by administration of obinutuzumab or rituximab; Patients will be considered treatment failures if the glucocorticoid dose has to be increased at any point during the 18-month study period because of a disease relapse. ***Disease relapse is defined as an increase in the BVAS/WG of ≥ 1 point accompanied by a decision on the part of the investigator to increase treatment for PR3-AAV***
- Time to treatment failure. ***Treatment failure is defined as the event when the glucocorticoid dose has to be increased at any point during the 18-month study period because of a disease relapse.***

Follow-up in the trial will continue until all patients have been followed for 18 months.

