3.1.2 Maintenance Phase

Patients who respond to treatment and achieve clinical remission will enter the maintenance phase and be evaluated every 3 months after the 6-month primary outcome assessment for a total of 18 months from the first dose. Patients will be considered treatment failures if the glucocorticoid dose has to be increased either during the prednisone taper or after remission because of a disease relapse or if any other treatment for ANCA-associated vasculitis is prescribed to treat a disease relapse. The patients who experienced treatment failure with detectable B cells (≥ 5 cells/ μ l) will be offered open-label obinutuzumab accompanied by one to three intravenous methylprednisolone pulses (1000 mg each) starting on or within 10 calendar days of obinutuzumab followed by oral glucocorticoid dosing at the discretion of the investigator (but not to exceed the original specified glucocorticoid tapering regimen) to control the disease. Patients who experience a treatment failure and B cells are still depleted should be treated according to best medical judgment. Patients who respond to the re-treatment and achieve clinical remission will enter the maintenance phase and be evaluated every 3 months until the entire study completes. Any patient who experiences treatment failure should continue with study follow-up visits per the schedule of assessments through the end of study.

All patients will be followed until they will have completed 18 months of follow-up or withdraw from the study prematurely.

The specific visit schedule is presented in Section 7, [Table 5](#). The study design is illustrated in [Figure 1](#).

[figure not shown]

Figure -1 PRRR Study Design

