9.8 Other Assessments or Analyses

The exploratory objectives are to compare:

- the number of relapses, defined as an increase in the BVAS/WG by at least one point accompanied by an increase in the intensity of treatment;
- the Glucocorticoid Toxicity Index (GTI) scores (Cumulative Worsening Score and Aggregate Improvement Score) over time;
- the cumulative glucocorticoid dose;
- the number of severe relapses, defined as the occurrence of life- or organ-threatening disease manifestation(s) or marked by an increase in the BVAS/WG of ≥ 3 and the investigator deems re-treatment is required;
- the changes from baseline in Vasculitis Damage Index (VDI) over time;
- the time to clinical remission;

- the changes in estimated glomerular filtration rate (eGFR);
- the proportion of patients achieving and maintaining complete peripheral blood B cell depletion (CD19+) at each study visit using high-sensitivity flow cytometry (HSFC);
- the kinetics of ANCA:
- Time to ANCA negativity
- Time to ANCA recurrence;
- the kinetic of recurrence of PR3-specific (autoantigen-specific) B cells after B cell depletion
- the changes from baseline on AAV patient reported outcome (AAV-PRO) assessment over time
- VCRC WG/MPA disease activity and transition assessment over time

The mechanistic study results will be analyzed and reported separately.

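### Treatment failure has two definitions, and the time-to-failure analysis in 9.7 uses the one that misses relapses treated with another agent alone

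*Combined protocol and SAP*

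**What the plan says.** Two definitions of treatment failure run through the document, and each is used consistently within its own kind of section.

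*Broad definition (design and conduct).* Section 3.1.2 counts a glucocorticoid increase for relapse, "or if any other treatment for ANCA-associated vasculitis is prescribed to treat a disease relapse". The synopsis study design and the paragraph run into heading 5.4 carry the same clause. Section 7.5 prints it in capitals: "OR IF ANY OTHER TREATMENT FOR ANCA-ASSOCIATED VASCULITIS IS PRESCRIBED TO TREAT A DISEASE RELAPSE".

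*Narrow definition (objectives and analysis).* The synopsis secondary objectives call patients "treatment failures if the glucocorticoid dose has to be increased at any point during the 18-month study period because of a disease relapse". Section 2.2 gives it as a formal definition: "Treatment failure is defined as the event when the glucocorticoid dose has to be increased at any point during the 18-month study period". The synopsis statistical methods and section 9.7 share this wording: "patients will be considered treatment failures if the glucocorticoid dose has to be increased because of a disease relapse either during the prednisone taper". Both also cover the time following remission. None of these four places mentions another agent.

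Section 9.7 compares time to failure through month 18 with a log-rank test and Kaplan-Meier plots, censoring patients without a failure when they were last known to be in follow-up. It also states: "No sensitivity analyses and adjustment for multiple comparisons will be conducted for the secondary endpoints".

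**The concern.** The event that the investigators act on is not the event that will be analysed. A relapse managed with a non-glucocorticoid agent alone is a failure when the trial decides what happens to the patient, but not when it compares the arms.

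Time to treatment failure is the only planned analysis close to the hypothesis in 3.3.1 that obinutuzumab delays relapse; section 9 has no time-to-relapse analysis. The remission endpoints in 9.7 are not a dependable backstop. They require a BVAS/WG of 0 off glucocorticoids, say nothing about other agents, and do not define the word sustained.

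The protocol leaves a route for such patients. Failures with detectable B cells are offered open-label obinutuzumab with methylprednisolone pulses, which would normally meet the narrow event as well. Failures who are still B-cell depleted are left to the clinician's judgment, with no glucocorticoid specified, and a patient may not take up the offered re-treatment.

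These groups need not be the same size in both arms. Section 3.3.1 expects longer depletion with obinutuzumab, so failures during depletion, and with them missed events, could be more common in that arm and flatter it. That direction is possible, not established.

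**Working it through.** The plan gives no event count, hazard ratio or power for this endpoint, so there is no figure to reproduce. The check compares the texts, followed by simple arithmetic on size.

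**1. The eight statements side by side**

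| Place | Glucocorticoid increase for relapse | Other vasculitis treatment for relapse |
|---|---|---|
| Synopsis, study design | counts | counts |
| 3.1.2 | counts | counts |
| 5.3/5.4 | counts | counts |
| 7.5 | counts | counts |
| Synopsis, secondary objectives | counts | absent |
| Synopsis, statistical methods | counts | absent |
| 2.2 | counts | absent |
| 9.7 | counts | absent |

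The split is four against four, and no other text reconciles it.

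**2. Does the relapse definition in 9.7 close the gap?** No. That section defines relapse as a BVAS/WG rise of at least 1 point "accompanied by a decision on the part of the investigator to increase treatment for PR3-AAV", which any agent can satisfy. But this defines relapse only. Failure still requires that the relapse led to more glucocorticoid.

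**3. One hypothetical patient.** Relapse at month 9, treated with another agent alone, no later glucocorticoid increase, followed to month 18:

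- 3.1.2: treatment failure at month 9.
- 9.8: counted as a relapse, since the rise was "accompanied by an increase in the intensity of treatment".
- 9.7: no event. The patient stays in the risk set for a further 18 − 9 = 9 months and is censored at month 18.

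If a glucocorticoid increase for relapse came later, 9.7 would count an event, but at the later date.

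**4. Size.** Inputs: 30 patients randomised 1:1 (synopsis, 9.2), so 30/2 = 15 per arm. The number k of affected patients in one arm is not in the documents; 0 to 3 is an assumed range. Shift in that arm's crude failure proportion = k/15:

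| k | Shift (points) |
|---|---|
| 0 | 0 |
| 1 | 6.7 |
| 2 | 13.3 |
| 3 | 20.0 |

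The between-arm difference shifts by the same amount if all affected patients are in one arm, and by 0 if they are equally divided.

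**5. Is this a power problem?** No. By Schoenfeld's approximation, power = Φ(√D × |ln HR| / 2 − 1.96), where D is the number of events. Assume, for illustration only, HR = 0.5 and 12 events under the broad definition: √12 × 0.693/2 − 1.96 = −0.76, so power is 22.4%. If 30% of those events drop out, D = 8.4 and power is 17.0%. Power is low under either definition, as the plan accepts. What the choice changes is the quantity being estimated.

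**The case against.** The strongest reply is that the affected group may be close to empty. A patient must relapse, receive another agent, and have no glucocorticoid increase at all. Section 3.3.1 describes relapse in this population as leading to re-treatment with glucocorticoids together with other agents. Section 3.3.3 lets the investigator raise the glucocorticoid dose, and nothing in 3.1.2 excludes glucocorticoids for depleted patients. The relapse is also not hidden, because 9.8 counts it. The bias argument needs three steps (longer depletion, more failures during it, treatment without glucocorticoids), and the documents support only the first, as a hypothesis. Longer time to relapse with obinutuzumab, which 3.3.1 also hypothesises, could offset it. Finally, a glucocorticoid-based event fits the aim of limiting steroid exposure, the endpoint is secondary with nominal p-values, and the later SAP could settle the matter.

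Much of this stands as a limit on impact: the group is probably small, and neither the size nor the direction of any bias can be determined from the documents. The crude proportion is also only a rough guide to a log-rank comparison, which depends on event timing.

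It does not remove the contradiction. The 9.8 count shows that a relapse occurred but does not correct the time-to-failure curve. That a SAP is still to be written is a reason to decide now: otherwise its author must choose between two protocol definitions, and a choice made after the month-6 results would no longer be clearly prespecified. The broad event is not merely a matter of taste, since it is the protocol's own wording and is closer to the relapse hypothesis.

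**Conclusion.** The concern holds. As written, 9.7 treats as failure-free a patient whom 3.1.2 classes as a treatment failure, and its relapse definition does not repair this. The wording conflict is certain. The practical effect is unknown and probably small: 6.7 points on a 15-patient arm's crude failure proportion for each affected patient, and 0 to 20.0 points over the assumed range of 0 to 3 in one arm. Those figures assume 15 analysed per arm and no later glucocorticoid increase in the affected patients. It should be fixed before the SAP is finalised; for a secondary endpoint in an unpowered proof-of-concept trial it is not critical.

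**What to change.** Use one event in the synopsis (secondary objectives and statistical methods), 2.2, 9.7 and the SAP: the first of a glucocorticoid increase for a disease relapse, or any other vasculitis treatment prescribed for a disease relapse, as 3.1.2 already has it. The SAP should name the date on which each component is counted.

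The glucocorticoid-only event can be kept as a supportive analysis under its own label. The sentence in 9.7 ruling out sensitivity analyses would then need amending.

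This changes the analysed event only, not who is offered re-treatment or how relapses are managed. The cost is wording. No new data are needed: 6.3.10 requires vasculitis treatments to be recorded as concomitant medications, 5.6 requires their dates and reasons, and 3.1.2 keeps failures in scheduled follow-up. The downside is slightly more events and slightly lower failure-free rates.

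### Treatment failure has no timing limit in 2.2 but two windows in 9.7, so a never-remitted patient who relapses after the taper is a failure in one and censored in the other

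*Combined protocol and SAP*

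**What the plan says.** The protocol defines treatment failure in three ways.

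- **Objectives (2.2 and synopsis, Secondary Objectives):** a patient fails if "the glucocorticoid dose has to be increased at any point during the 18-month study period because of a disease relapse". There is no timing restriction.
- **Analysis (9.7 and synopsis, Statistical Methods):** the glucocorticoid increase must be "because of a disease relapse either during the prednisone taper or after the remission is achieved".
- **Conduct (3.1.2, repeated in the synopsis design text, 5.4 and 7.5):** the increase must come "either during the prednisone taper or after remission because of a disease relapse or if any other treatment for ANCA-associated vasculitis is prescribed", again for relapse. This has the two windows and adds a limb for other treatment that neither 2.2 nor 9.7 contains.

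Section 9.7 also says "A disease relapse is defined as an increase in the BVAS/WG of 1 point or more", together with an investigator's decision to increase treatment. Patients without a failure are censored at last known follow-up. The comparison is by log-rank test with Kaplan-Meier plots through 18 months, and 9.7 rules out sensitivity analyses for the secondary endpoints.

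**The concern.** The two windows in 9.7 do not cover the whole 18 months. Between the end of the taper and the first remission there is an interval in which a relapse-driven glucocorticoid increase meets 2.2 but not 9.7. The patients in that interval are those whom the study drug has not brought into remission. Scoring them as failure-free would flatter whichever drug leaves more patients unremitted.

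This is the only time-to-event secondary endpoint, and 3.3.1 says the trial will test whether obinutuzumab lengthens time to relapse. The trial is to be read through trends and nominal p-values, and no planned analysis uses the other definition, so the effect would not show itself.

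**Working it through.** The documents give no event count, hazard ratio or power for this endpoint, so there is no planned figure to reproduce. The check is a comparison of texts, followed by illustrations on stated assumptions.

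**1. Trace one patient.** Suppose prednisone has stopped at week 17 (Table 1), BVAS/WG is still above 0, and remission has never been reached. At month 5 BVAS/WG rises by 1 point and glucocorticoids are increased for relapse.
- Relapse definition: met, since prior remission is not required.
- 2.2: failure at month 5.
- 9.7: the taper is over and remission has not been achieved, so neither window applies. The patient is censored at last known follow-up. If the patient later remits and relapses, the failure is counted at that later date.

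**2. Length of the gap.** Take the taper as starting on day 0, so week 16 ends on day 16 × 7 = 112. To month 6: 180 − 112 = 68 days. To month 18, for a patient who never remits: 540 − 112 = 428 days.

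**3. How many patients.** The documents do not say. Section 1 reports that 29% of PR3 patients in the earlier rituximab-versus-cyclophosphamide trial failed its primary outcome through active disease. Applied here, 0.29 × 15 = 4.35 per arm. This is a loose upper guide: it pools both drugs and can include failures that 9.7 would count.

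**4. Direction.** For one arm let q be the share not remitting, f the 18-month probability of a relapse-driven increase in non-remitters, r the same in remitters, and g the share of non-remitter events that fall in the gap. With complete follow-up and no late remission:
- 2.2 failure rate = q·f + (1 − q)·r
- 9.7 failure rate = q·f·(1 − g) + (1 − q)·r
- Events lost = q·f·g

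If f and g are equal in both arms, the arm with the larger q loses more events.

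**5. Size, on assumed values.** Take q = 0.29 for rituximab and 0.15 for obinutuzumab, f = 0.80, and r = 0.30 in both arms. None of these is a design value.
- 2.2: 0.232 + 0.213 = 44.5% v 0.120 + 0.255 = 37.5%; difference +7.0 points (rituximab minus obinutuzumab).
- 9.7, g = 1: 21.3% v 25.5%; difference −4.2 points.
- 9.7, g = 0.5: 32.9% v 31.5%; difference +1.4 points.
- The sign changes only if g exceeds 7.0 / (0.14 × 80) = 0.625. With f = 0.50 the 2.2 difference is 35.8% − 33.0% = +2.8 points, and the threshold is 2.8 / (0.14 × 50) = 0.40.
- With g = 1 but r = 0.20 for obinutuzumab: 21.3% − 0.85 × 20% = +4.3 points, no reversal.

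The standard error of a difference near 21% v 25% with 15 per arm is √(0.213 × 0.787/15 + 0.255 × 0.745/15) ≈ 15 points.

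**6. Sensitivity of the test, on invented event times.** Take 15 per arm, with 3 obinutuzumab and 7 rituximab failures under 2.2: log-rank p = 0.10. If 1, 2 or 3 of the rituximab failures fall in the gap and are censored at day 540, p becomes 0.21, 0.39 or 0.66.

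**The case against.** **The gap may be nearly empty.** Sections 3.1.1 and 5.6.2 state the stop at 16 to 17 weeks only for patients in remission without flares. If an unremitted patient's taper is prolonged, an increase could still be read as occurring during the taper. The BVAS/WG instructions in Appendix 5 also treat features lasting more than 3 months as damage, so items that merely persist from baseline should no longer score by week 17. Both points stand and shrink the gap. Neither closes it: 5.6.2 prescribes one regimen to all randomized patients, and Table 1 ends at zero.

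**The authors may have meant the windows to be exhaustive.** That is plausible. If so, the 2.2 wording states the intent without cost.

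**A reader might infer that the comparison will point the wrong way.** The documents do not support this. The −4.2 points above come from placing every non-remitter event in the gap and giving remitters the same 30% risk in both arms, which sits badly with the trial's own hypothesis. A reader might also halve the 29% and conclude that 0.29 × 0.5 = 14.5 points of failure go uncounted in each arm. That rests on an invented flare rate and on the upper-guide figure from Section 1, and an equal loss in both arms need not bias the difference.

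**The stakes are limited.** This is one secondary endpoint in a study that 9.2 calls unpowered. Non-remission still shows in complete remission at months 6, 12 and 18, and 9.8 reports relapse counts and time to clinical remission. This stands and bears on severity, not on whether the texts agree.

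**Conclusion.** The inconsistency is literal and in current text. Following 9.7 as written would censor, or count late, some patients who are failures under 2.2. Only patients not brought into remission lose events, so any bias is expected to favour the arm with more non-remitters, provided flare risk and timing among non-remitters are similar in the two arms.

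The number affected cannot be derived from the documents and is probably small. The log-rank figures show that one to three events could matter at this sample size; they do not show that such events will occur. The primary endpoint is untouched. The definition should be settled before the SAP is final.

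**What to change.** In 9.7, the synopsis statistical methods and the separate SAP announced in 9.1, define the time-to-treatment-failure event as a glucocorticoid increase "at any point during the 18-month study period because of a disease relapse", and derive it regardless of prior remission status. The cost is one phrase. No new data are needed, since BVAS/WG and medication use are already recorded throughout.

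Separately, 3.1.2, 5.4, 7.5 and the synopsis design text use the restricted windows and add the other-treatment limb missing from 2.2 and 9.7. A relapse treated only with a non-glucocorticoid drug is therefore a failure there but not in the objective or the analysis. These passages must be reconciled with 2.2 and 9.7. They also govern the offer of open-label re-treatment, so how they are worded is a clinical decision for the sponsor, and no re-treatment rule is proposed here.
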